9.3 Analyses

The main analysis will be undertaken at completion of the project, using the data analyses from the trial. There will be two components to the analysis: a within trial analysis and a model-based analysis.

Model-based analysis - a preliminary modelling exercise will be carried out at the beginning of the study and will be populated and refined during the pilot to prepare for the end of trial analysis.

A decision analytic model will be used to allow the extrapolation of cost and effectiveness parameters beyond the data observed in the clinical trial (and to allow extrapolation to other settings). The model will, therefore, consider treatment over total disease duration and will include surgical treatments provided in the longer term. An individual sampling model (such as a Markov model) or similar model to ensure time to event can be analysed. A preliminary model-based analysis will be conducted during the initial months of the study, using all available data and highlighting areas of uncertainty to be targeted during the trial – this will be revisited during the pilot stage and draw upon follow-up data up to 18 months. This will utilise published data and assumptions to predict costs and benefits into the long-term. The analysis will then be repeated in the last 12 months of the study using the main trial and follow-up data, but still predicting costs and effects beyond the trial end.

Results of all economic analyses will be presented using cost-effectiveness acceptability curves to reflect sampling variation and uncertainties in the appropriate threshold cost-effectiveness value. We shall also use simple and probabilistic sensitivity analyses to explore the robustness of these results to plausible variations in key assumptions and variations in the analytical methods used, and to consider the broader issue of the generalisability of the results.

10. TISSUE SAMPLE COLLECTION

Tissue samples must be collected in accordance with the SMALL Trial Tissue Sample Collection Guidelines.

Principal Investigators are asked to nominate one individual at their site to act as a Lead Pathologist. The Lead Pathologist will be provided with the SMALL Trial Tissue Sample Collection Guidelines describing the labelling and shipment of samples.

A representative formalin fixed paraffin embedded tumour block from the VAE will be collected for all consenting patients recruited to the VAE arm of the trial, plus a representative block from any subsequent confirmed ipsilateral recurrence will be submitted to the Human Biomaterials Resource Centre (HBRC) for future ethically approved research.

For further details please refer to the SMALL Trial Tissue Sample Collection Guidelines.

All material must be sent to:

[name] Human Biomaterials Resource Centre (HBRC) University of Birmingham [name]

☎ [name]☑ [contact]

If the tissue sample is urgently needed for subsequent re-assessment by the local Pathology Department, please contact the SMALL Trial Office who will arrange for immediate retrieval of the material and return.

Please be aware that it will be the responsibility of the local research team to obtain their patient's pathology material if the material is stored at a separate site to the registering hospital.

Pathology Departments will receive a per-patient payment for supplying the requested samples.

11. MAMMOGRAPHIC IMAGE LIBRARY

The trial will generate a library of anonymised mammographic and ultrasound images. The aim of any future image studies would be to identify potential radiological features that might identify cases where minimally invasive treatment was associated with early local recurrence (i.e. features predicting for possible incomplete excision with VAE).

Retrospective collection of radiological images is notoriously complex and incomplete and the raw (unprocessed) images, which are not routinely stored on hospital Picture Archive Computer Stores (or a local equivalent platform) are needed for any computer based analysis, therefore data needs to be captured in real time, as much as possible. Sites will be supplied with bespoke image collection software tools³⁸. This will provide:

- De-identification with a pseudonym, Digital Imaging and Communications in Medicine (DICOM) Supplement 142 compliant, de-identification process that recognises the primary identifier (usually the NHS number) and always replicates the original pseudonym. This means that any new images from a recognised trial patient will always be allocated to the correct file within the data store
- Automatic uploading via N3, the secure NHS network
- Mark up and remote reading on any PC connected to the internet but specifically the diagnostic quality monitors attached to the work stations regularly used and quality assured for the breast screening programme

SMALL trial patients will be appropriately tagged within the store to ensure that images can be subsequently associated with outcome data from the trial site.

The image library is maintained and managed by the Scientific Computing section based at Royal Surrey County Hospital. The de-identified image and data will be stored on the cloud.

Participating sites which do not use Picture Archiving Computer Stores or an equivalent platform, should submit de-identified images for review on CD via post to the Scientific Computing section at Royal Surrey County Hospital, including the patient's TNO, date of birth and date of mammogram only as identifiers.

12. ADVERSE EVENT REPORTING

The collection and reporting of Adverse Events (AEs) will be in accordance with the UK Policy Framework for Health and Social Care Research and the requirements of the National Research Ethics Service (NRES). Definitions of different types of AE are listed in Appendix 2. The Investigator should assess the seriousness and causality (relatedness) of all AEs experienced by the patient (this should be documented in the source data) with reference to the protocol.

12.1 Reporting Requirements

12.1.1 Adverse Events

AEs (see Appendix 2 for definitions) are commonly encountered in patients receiving treatment for breast cancer. The safety of these treatments is already well characterised, therefore only related AEs experienced as a direct result of the trial protocol will be reported.

12.1.2 Serious Adverse Advents

Investigators should report AEs that meet the definition of an SAE (see Appendix 2 for definition) and are not excluded from the reporting process as described below.

12.1.2.1 Expected Serious Adverse Events

The following are regarded as expected SAEs for the purpose of the trial and should not be reported on an SAE form:

- Hospitalisation for primary surgery
- Haematoma, wound infection or seroma, as a result of primary breast surgery, unless the condition is life threatening or proves fatal
- SAEs relating to breast reconstruction
- SAEs relating to adjuvant treatment for breast primary cancer or recurrence
- SAEs that are related to symptoms or progression of the patient's cancer
- Death from cancer or from a pre-existing medical condition

This is not an exclusive list and Investigators should only report SAEs which are attributable to the trial protocol.

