7.2.2.1 Vacuum assisted excision

Please refer to the SMALL Radiology Manual for detailed guidance on the VAE procedure. Patients randomised to this arm of the trial will undergo VAE of their breast cancer under local anaesthesia as an out-patient procedure. It is expected that VAE will be performed within 31 days of randomisation. VAE may be carried out under either ultrasound or stereotactic guidance. All cores taken at VAE should be submitted for histopathological assessment, with number of cores and total weight recorded on the CRF. VAE should be carried out by appropriately-trained individuals carrying this out as part of their routine clinical practice. Post-VAE a marker clip should be inserted and a post-VAE mammogram carried out (lateral/mediolateral oblique and cranio-caudal views). The procedure report should stipulate the needle gauge used, number of cores taken and the type of marker clip placed in the breast, together with the operator's impression of the completeness of excision. The post-VAE mammogram report should state whether the lesion remains visible. If no lesion is visible then complete excision of the lesion is assumed. If the lesion remains visible then surgical excision will be required, in these cases please also forward a copy of the patient's anonymised pathology report to the SMALL Trial Office.

If interpretation of the post-VAE mammogram is unclear due to the presence of haematoma then a repeat mammogram should be carried out at 4 weeks post-procedure. If haematoma remains present at this stage then repeat ultrasound should be carried out with aspiration of the haematoma. Subsequently a further repeat mammogram should be carried out. If at this stage the lesion is resolved then complete excision is assumed. A persistent lesion should be assumed to be residual disease and the patient should proceed to surgical excision.

Where there is uncertainty at a local level regarding completeness of excision, a radiological second opinion can be provided through the Radiological Second Opinion Service (see below, Section 7.2.3.3).

Patients undergoing VAE only in the VAE arm will not undergo any axillary procedure in addition to their axillary ultrasound carried out as part of their diagnostic assessment. Patients proceeding from VAE to surgical treatment due to radiological assessment of incomplete excision should undergo axillary staging using sentinel lymph node biopsy.

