12.2.2 Trial Office

On receipt of an SAE Form seriousness and causality will be determined independently by a Clinical Coordinator. An SAE judged by the Investigator or Clinical Coordinator to have a reasonable causal relationship with the trial treatment will be regarded as a related SAE. The Clinical Coordinator will also assess all related SAEs for expectedness. If the event is unexpected (i.e. is not defined in the protocol as an expected event) it will be classified as an unexpected and related SAE.

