12.2.5 Data Monitoring Committee

The independent Data Monitoring Committee (DMC) will review all SAEs.

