16.2.2 Definition of Secondary outcome measures

Complications arising from surgery or VAE

This is defined as complications occurring within 30 days of protocol defined surgery or VAE. Possible complications are expected to include seroma, haematoma, wound infections, delayed wound healing, skin flaps necrosis, nipple necrosis, wound dehiscence, in hospital complications, hospital readmission and unplanned re-operations, and these are defined in Appendix 4.

Time to ipsilateral breast cancer recurrence

This is defined in whole days as the time from randomisation until first report of ipsilateral invasive disease. Randomised patients with no evidence of disease will be censored at the date of last clear mammogram or date of death.

Time to development of contralateral invasive breast cancer

This is defined in whole days as time from randomisation until first report of contralateral invasive disease. Randomised patients with no evidence of disease will be censored at the date of last clear mammogram or date of death.

Overall survival time

This is defined in whole days as time from randomisation until date of death from any cause. Patients who remain alive during the course of the study will be censored at the date last known to be alive.

Quality of life

The assessment utilities being used are defined in Section 8.1. These will all be scored at each timepoint utilising the specific scoring schemes for each type of questionnaire which will produce scores across multiple themes and domains.

QALY

This will be calculated from the EQ5D QoL questionnaire and will be utilised in the Health Economic analysis (see Section 9).

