APPENDIX 2 – DEFINITION OF ADVERSE EVENTS

Adverse Event

Any untoward medical occurrence in a patient or clinical trial subject participating in the trial which does not necessarily have a causal relationship with the treatment received.

Comment:

An AE can therefore be any unfavourable and unintended sign (including abnormal laboratory findings), symptom or disease temporally associated with the use of a medicinal product, whether or not related to the medicinal product.

Related Event

An event which resulted from the administration of any of the research procedures.

Serious Adverse Event

An untoward occurrence that:

- Results in death (unrelated to original cancer)
- Is life-threatening*
- Requires hospitalisation** or prolongation of existing hospitalisation
- Results in persistent or significant disability or incapacity
- · Consists of a congenital anomaly/ birth defect
- Or is otherwise considered medically significant by the Investigator***

Comments:

The term severe is often used to describe the intensity (severity) of a specific event. This is not the same as serious, which is based on patients/event outcome or action criteria.

* Life threatening in the definition of an SAE refers to an event in which the patient was at risk of death at the time of the event; it does not refer to an event that hypothetically might have caused death if it were more severe.

**Hospitalisation is defined as an unplanned, formal inpatient admission, even if the hospitalisation is a precautionary measure for continued observation. Thus hospitalisation for protocol treatment (e.g. line insertion), elective procedures (unless brought forward because of worsening symptoms) or for social reasons (e.g. respite care) are not regarded as an SAE.

*** Medical judgment should be exercised in deciding whether an AE is serious in other situations. Important AEs that are not immediately life threatening or do not result in death or hospitalisation but may jeopardise the subject or may require intervention to prevent one of the other outcomes listed in the definition above, should be considered serious.

Unexpected and Related Event

An event which meets the definition of both an Unexpected Event and a Related Event.

Unexpected Event

The type of event that is not listed in the protocol as an expected occurrence.

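### Non-life-threatening haematoma, wound infection and seroma are kept off the SAE form after primary breast surgery but not after VAE, and the protocol is inconsistent on whether they are expected after VAE

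*Protocol*

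**What the plan says.** Section 12.1.2 requires SAEs to be reported unless they are excluded. Section 12.1.2.1 gives the exclusions: "The following are regarded as expected SAEs for the purpose of the trial and should not be reported on an SAE form". One item is "Haematoma, wound infection or seroma, as a result of primary breast surgery, unless the condition is life threatening or proves fatal". No item mentions VAE. The list ends: "This is not an exclusive list and Investigators should only report SAEs which are attributable to the trial protocol".

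At the Trial Office (12.2.2), related SAEs are assessed for expectedness: "If the event is unexpected (i.e. is not defined in the protocol as an expected event"), the event is classed as unexpected and related. Section 12.2.3.1 sends that class to the ethics committee and Sponsor within 15 days. Appendix 2 defines an unexpected event as "The type of event that is not listed in the protocol as an expected occurrence".

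On oversight, 12.2.5 states: "The independent Data Monitoring Committee (DMC) will review all SAEs".

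Complications are also a secondary outcome (16.2.2): "This is defined as complications occurring within 30 days of protocol defined surgery or VAE". The same paragraph names seroma, haematoma and wound infection among the complications to be expected.

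**The concern.** The exemption is tied to the control procedure. Arm A is surgery and Arm B is VAE (6.2.2), 13.1 provides separate procedure forms, and 16.2.2 names the two side by side. A site following 12.1.2.1 to the letter would therefore withhold an SAE form for an admission with wound infection after surgery and submit one for the same admission after VAE. No reason for the difference is given.

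Two things are at stake. First, the DMC may recommend stopping on patient-safety grounds (17.5), and for these event types the SAE listing it sees would differ between arms because of the reporting rule, whatever the procedures themselves do. Second, a haematoma after VAE could enter the 15-day route as unexpected although the protocol foresees it. Section 7.2.2.1 sets out an imaging pathway that begins "If interpretation of the post-VAE mammogram is unclear due to the presence of haematoma".

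**Working it through.** The protocol states no figure to reproduce. The check sets the sections side by side.

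**Handling of a serious haematoma, wound infection or seroma**

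| Situation | SAE form? | Expected? |
|---|---|---|
| After primary surgery, not life-threatening or fatal | No (12.1.2.1) | Yes (12.1.2.1) |
| After VAE, not life-threatening or fatal | Yes, because not excluded (12.1.2, 12.1.2.1) | No, if 12.2.2 is applied to the 12.1.2.1 list; yes, on 16.2.2 and Appendix 2 |
| After surgery that follows incomplete VAE or regrading | Unclear | Unclear |
| Life-threatening or fatal, either arm | Yes | Not covered by the exemption |

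**Expectedness after VAE.** Sections 12.1.2.1 and 12.2.2 together point to unexpected, because the only list headed as expected SAEs leaves VAE out. Four places point to expected:
- 16.2.2 names these complications as expected for either procedure.
- Appendix 2 judges by type of event, and the types are listed.
- 7.2.2.1 anticipates haematoma after VAE.
- 12.1.2.1 says its own list is not exclusive.

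The protocol does not say which governs.

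**Crossover to surgery.** Women with a lesion still visible after VAE, or regraded to grade 3, go on to surgery (7.2.2.1). Section 16.7 assumes 20% re-excision, which in the VAE arm is 0.20 × 533 = 106.6, about 107 women. Nothing says whether that operation is primary breast surgery for the purpose of the exemption.

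**The backstop.** Section 12.1.3 says all AEs are documented and reported except those listed above it. Read literally, this removes the exempt surgery-arm events from AE reporting as well as from the SAE form. That conflicts with 7.1.6, the surgical procedure form in 13.1, and the outcome in 16.2.2, all of which require them.

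**Illustration of size.** Assumption: the same rate in both arms of serious, not life-threatening haematoma, infection or seroma after the randomised procedure. The protocol gives no such rate, so a range is shown. Arm sizes are from 16.7 (533 VAE, 267 surgery). Formula: expected events = rate × arm size.

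| Assumed rate | VAE, on SAE forms | Surgery, true events | Surgery, on SAE forms |
|---|---|---|---|
| 1% | 0.01 × 533 = 5.3 | 0.01 × 267 = 2.7 | 0 |
| 2% | 0.02 × 533 = 10.7 | 0.02 × 267 = 5.3 | 0 |
| 5% | 0.05 × 533 = 26.7 | 0.05 × 267 = 13.4 | 0 |

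With equal true rates, the SAE forms for these event types would all come from the VAE arm. The Appendix 4 complications table would show about 2:1, matching the allocation.

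**The case against.** The strongest reply is that the SAE listing is not where these complications are compared. Appendix 4 grades seroma, haematoma and wound infection by severity, up to surgical drainage or evacuation, and records readmission. These data are collected in both arms (7.1.6, 7.2.5, 13.1) and reported descriptively for both (16.3). Section 16.5 gives the DMC complications data by allocation and all adverse events. The protocol plans no formal comparison of SAE counts. This stands, and it is why the point is minor. It does not correct the SAE listing itself, and the wording of 12.1.3 weakens it.

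A reader might also infer that VAE events are definitely classed as unexpected and sent to the ethics committee. The documents do not support that. Section 12.2.2 refers to the protocol as a whole, and 16.2.2 with Appendix 2 gives good grounds for expected. What can be shown is an inconsistency.

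A third argument is that lighter reporting for standard surgery and fuller reporting for the newer procedure is a defensible, cautious choice. Section 12.1.1 rests reduced reporting on well-characterised safety. That is fair, but the protocol does not state it as the reason for this difference, and it would not make the counts comparable.

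Finally, equal rates are only an assumption. VAE is an out-patient procedure under local anaesthesia, and hospitalisation counts as serious only if it is an unplanned inpatient admission (Appendix 2). True rates may be lower after VAE.

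**Conclusion.** The concern holds as a minor inconsistency in safety reporting. Taken literally, 12.1.2.1 makes SAE ascertainment differ by arm for three event types when they are not life-threatening or fatal. Expectedness after VAE is unresolved, the status of surgery after VAE is undefined, and 12.1.3 conflicts with the complications outcome.

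It would go too far to conclude that SAE counts as a whole cannot be compared, or that the DMC will be misled. Life-threatening and fatal cases are reportable in both arms, other SAE types are not touched by this clause, and the DMC also receives complications by arm. No primary outcome is affected. The complications outcome is at risk only if sites apply 12.1.3 literally.

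The literal effect is 5 to 27 VAE events on SAE forms against none for surgery, at assumed rates of 1% to 5%. This rests on equal rates in the two arms, on sites following the wording exactly, and on VAE not being read as primary breast surgery.

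**What to change.** Reconcile 12.1.2.1, 12.1.3, 12.2.2, 16.2.2 and Appendix 2 so that one SAE reporting and expectedness rule covers surgery, VAE and any subsequent protocol surgery. The three event types, when not life-threatening or fatal, should be either exempt in both arms or reportable in both. Add to 12.1.3 that Appendix 4 complications are always recorded, whether or not an SAE form is needed.

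If the difference between arms is intended, state it with its reason, leave these event types out of by-arm SAE comparisons, and rely on the Appendix 4 table for them.

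The cost is a clause in 12.1.2.1, a sentence in 12.1.3, matching edits on expectedness, and the SAE form guidance. No treatment, endpoint or sample size changes. Lifting the exemption brings somewhat more SAE forms from the surgery arm. Extending it to VAE brings fewer expedited reports for the newer procedure, which the sponsor should weigh before choosing that option.

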12.2 Reporting Procedure

12.2.1 Site

12.2.1.1 Adverse Events

Protocol-related AEs should be recorded in the AE section of the Treatment Form and Annual Followup Form with reference to the defined Surgical Complications and Definitions (see Appendix 4).

SAEs will be reviewed using the Common Terminology Criteria for Adverse Events (CTCAE), version 4.0 (see Appendix 3). Any SAEs experienced by the patient but not included in the CTCAE should be graded by an Investigator and recorded on the AE Form using a scale of (1) mild, (2) moderate or (3) severe. For each sign/symptom, the highest grade observed since the last visit should be recorded.

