APPENDIX 4 – SURGICAL COMPLICATIONS & DEFINITIONS

Post-operative complications occurring within 30 days;

- 1. Seroma (breast/axilla) a collection of serosanginous fluid in the wound
 - a. Requiring aspiration 1-2 times
 - b. Requiring aspiration 3 or more times
- 2. Haematoma (breast/axilla) a collection of blood in the wound
 - a. Minor (conservative management)
 - b. Major 1 requiring evacuation in clinic +/- US guidance (no GA)
 - c. Major 2 requiring surgical evacuation (GA)
- 3. Wound infection (breast/axilla)
 - a. Minor (oral antibiotics)(breast/axilla)
 - b. Major 1 (iv antibiotics)(breast/axilla)
 - c. Major 2 (surgical drainage +/- debridement)(breast/axilla)
- 4. Delayed wound healing/skin flap necrosis
 - a. Minor (conservative management)
 - b. Major 1 requiring surgical debridement in clinic (no GA)
 - c. Major 2 requiring surgical debridement in theatre (GA)
- 5. Nipple necrosis
 - a. Minor (conservative management)
 - b. Major 1 (requiring debridement)
 - c. Major 2 (complete NAC loss)
- 6. Wound dehiscence (breast/axilla)
 - a. Minor (conservative management)(breast/axilla)
 - b. Major (requiring return to theatre)(breast/axilla)
- 7. In-hospital complication (including systemic complications
 - a. DVT/PE/MI/LRTI/UTI/transfusion/unplanned HDU/ITU admission
- 8. Readmission to hospital within 30 days
 - a. No
 - b. Yes, for complication listed above (1-7)
 - c. Yes, for other reason

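### A death soon after a trial procedure that the site attributes to pre-existing disease is exempt from SAE reporting, so it bypasses independent causality review and the ethics committee route

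*Protocol*

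**What the plan says.** Protocol section 12.1.2 asks for every event meeting the SAE definition to be reported unless it is excluded. Appendix 2 gives the criterion for death: "Results in death (unrelated to original cancer". Section 12.1.2.1 then sets out the exclusions, introduced by "The following are regarded as expected SAEs for the purpose of the trial and should not be reported on an SAE form". One item is "Death from cancer or from a pre-existing medical condition", with nothing further attached. Another covers haematoma, wound infection and seroma after primary breast surgery, and it carries the limit "unless the condition is life threatening or proves fatal". The section closes with a general rule: "Investigators should only report SAEs which are attributable to the trial protocol".

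The same list governs expectedness. Section 12.2.2 has the Clinical Coordinator judge related SAEs with the test "If the event is unexpected (i.e. is not defined in the protocol as an expected event".

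The 30-day complications outcome is defined in section 16.2.2 and in Appendix 4, which opens with "Post-operative complications occurring within 30 days" and has eight numbered categories. Separately, sections 7.1.7 and 7.2.6 require a Death Form for every death in both arms, and section 13.1 lists its content as date and cause.

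**The concern.** The exemption depends on the cause of death that the site assigns, and the site knows which treatment the woman received. In a woman with known disease who dies days after a procedure, that attribution is often uncertain. It is the kind of judgement that independent review of SAEs is meant to check. Here the attribution is made first, and it decides whether the check takes place.

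Avoiding a general anaesthetic and an open procedure is one of the benefits the protocol gives for VAE (section 1.2.1). Deaths soon after a procedure are the most serious information the trial can collect on that claim, in either arm. They should reach the bodies that oversee safety with an independent view on causality, and the 30-day safety outcome should have a place for them.

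**Working it through.** There is no figure to reproduce, so the check is to follow one event through the text: a woman with known heart disease dies within 30 days of a trial procedure, and the site gives her heart disease as the cause.

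1. **Does it meet the SAE definition?** Yes. Under Appendix 2 it is a death not related to the original cancer.
2. **Does it go on an SAE form?** No. Section 12.1.2.1 exempts it, however soon after the procedure it occurs. The closing rule on attribution narrows reporting further and does not bring a listed event back.
3. **Is it documented as an AE instead?** Not by rule. Section 12.1.3 leaves the listed events out of AE documentation as well.
4. **Is causality reviewed independently?** No. Under section 12.2.2 the Clinical Coordinator's review begins when an SAE form arrives. The 24-hour deadline in section 12.2.1.2 also applies only to events that need the form.
5. **Can it reach the ethics committee as unexpected and related?** No. Being on the list makes it expected under section 12.2.2, and section 12.2.3.1 sends on only unexpected and related SAEs.
6. **Does the DMC see it as an SAE?** Section 12.2.5 has the DMC review all SAEs, but no route is stated by which an event without an SAE form would be presented as one. Section 16.5 lists the data for the DMC and does not name deaths.
7. **Does the 30-day outcome count it?** Only in part. Appendix 4 item 7 covers in-hospital events such as MI and PE, and item 8 covers readmission, so a precipitating event may be counted there. The fatal outcome has no category in Appendix 4 or in section 16.2.2. Surgery is mostly day-case (section 1.1) and VAE is an out-patient procedure (section 7.2.2.1), so a death at home without readmission may match none of the eight items.
8. **Where is it recorded?** On the Death Form, with date and cause, and as an event in overall survival (section 16.2.2). Relatedness to the procedure is not among the form's listed content.

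Within section 12.1.2.1, a fatal wound infection after primary breast surgery returns to the SAE form through the stated exception. The item that concerns death itself has no such exception.

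The exposure can be stated from section 16.7. There are 800 planned first procedures and, at the assumed 20% re-excision rate, about 0.20 × 800 = 160 second procedures, of which 0.20 × 533 ≈ 107 are in the VAE arm. The documents give no peri-procedural death rate, so an expected number of affected deaths cannot be derived from them.

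**The case against.** The strongest reply is that the exemption turns on cause. A death the investigator judges to result from anaesthesia or surgery is not a death from a pre-existing condition, and section 12.1.2.1 expects events attributable to the protocol to be reported. This stands as far as it goes. A reader might infer that the rule removes anaesthetic or surgical deaths in general from reporting, and the text does not support that. What remains is the mixed-cause death, where the site's attribution settles the matter with no independent check.

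It can also be said that Appendix 2 and section 12.1.2.1 do not contradict each other, because section 12.1.2 allows exclusions and section 12.1.1 explains why reporting is limited. That is right: this is a chosen reporting rule, drawn too widely.

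A further reply is that the death is captured elsewhere. The Death Form is due immediately, the opening of section 12 has the investigator document seriousness and causality in the source data, and the DMC receives safety data and may recommend stopping on safety grounds (section 17.5). It would therefore be wrong to infer that such deaths are lost to the trial, or that nothing about them could appear as a complication. Appendix 4 items 7 and 8 can record the event leading to death, and section 16.2.2 describes what complications are expected to include, so it need not be read as a closed list. None of this supplies independent causality review or a category for the death itself.

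Finally, a reader might take the three-level scale in section 12.2.1.1 as a second gap through which fatal SAEs leave the SAE form. That section concerns grading. Section 12.2.1.2 still requires the SAE Form for every serious event that is not excluded.

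**Conclusion.** The point holds in a limited form. The death exemption in section 12.1.2.1 has no limit on timing or possible relatedness. A peri-procedural death attributed to pre-existing disease therefore bypasses the 24-hour SAE report, independent causality review, the unexpected-and-related route to the ethics committee and the DMC's SAE review. The 30-day complications outcome may hold the precipitating event but has no category for the death.

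The gap is narrow. It concerns only deaths that the site assigns to an exempt cause, all of which remain visible on the Death Form and in overall survival. The number is likely to be small, but no rate in the documents allows it to be estimated. Complications are reported descriptively without testing (section 16.3), so neither co-primary analysis nor the power calculation is affected. The case for change rests on patient safety and on how little the change costs. It assumes the SAE form is the only trigger for the steps in sections 12.2.1.2 to 12.2.3.1, which is what the protocol states.

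**What to change.** 1. In section 12.1.2.1, state that the death exemption does not cover any death within 30 days of VAE, surgery or a second procedure, nor any later death judged possibly related to one of them. Such deaths go on an SAE form for independent causality review and are not classed in advance as expected.
2. In Appendix 4 and the complications definition in section 16.2.2, add death within 30 days from any cause.
3. Optional and secondary: give the breast reconstruction item in section 12.1.2.1 the same exception for life-threatening or fatal cases that the haematoma, infection and seroma item already has.

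The 30-day window and the exception for fatal cases are already in the protocol, so no new concept is needed. The cost is a few words in three places and at most a few extra SAE forms. Treatment, sample size and the primary analyses do not change.
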